6.1.4 Procedures at time of discharge/death

Participants will be discharged by site study staff when they meet criteria for discharge from the newborn unit. The following data will be documented on the eCRF within 24h of discharge or death.

- Date and time of discharge/death
- Cause of death if died
- Diagnoses at time of discharge/death
- Most recent weight before discharge/death
- Details of feeding at time of discharge/death
- SARS-CoV-2 signs/symptoms and testing status/results for mothers and babies recruited after 25 March 2020

At time of discharge, parents/caregivers will be provided with an illustrated handout on neonatal danger signs and instructed to contact the site study team or seek medical help if their baby becomes unwell before the day 28-30 follow-up appointment. Families will be provided with phone numbers to contact the study team and a study participant ID card.

6.1.5 Procedures at follow-up

At the 28-30-day follow-up visit, we will record:

- Breastfeeding status
- Anthropometric measures (weight, OFC, length)

- SARS-CoV-2 signs/symptoms and testing status/results for mothers and babies recruited after 25 March 2020

For participants at KNRH EH and JH, repeat cUS will be performed at the 28-30-day visit (see Section 6.1.6 for additional details). For the MIRI, trained study staff will administer a brief, validated set of questions to all mothers at the 28-30-day visit.

6.1.6 Cranial ultrasound imaging

For participants at KNRH and JH, cUS will be performed on days 1, 3, 7, and 28-30 to examine for the presence of intracerebral pathology associated with morbidity and mortality amongst preterm infants. This includes intraventricular haemorrhage, cystic degeneration, and later hydrocephalus. The study paediatrician or medical officer at the respective sites will perform cUS using a portable ultrasound machine (Sonosite Edge II). Both standard and linear probes will be used to assess for abnormalities according to a defined protocol and to include a minimum of 11 coronal and sagittal views. Images will be read by an independent expert.

6.2 Economic Evaluation

For cost data collection for households, the project, and the hospital perspectives, multiple data sources will be triangulated to arrive at best estimates. Where possible, resource use and unit costs will be collected and presented separately, although some costs, such as out-of-pocket payments for transport do not permit this. Household costs will be collected through surveys that will be conducted with a sample of the caretakers at the time of discharge and during follow-up visits.

Project costs will be collected prospectively from project accounts using an Excel-based costing tool. These will be supplemented with time sheets and key informant interviews to inform allocation of joint costs. Direct and indirect costs incurred by providers will be collected prospectively and retrospectively using key informant interviews, facility audits, direct observations, and time-use surveys. As necessary, we may supplement secondary data on costs of treating subsequent conditions with limited primary data collection in the Ugandan study hospitals. We will model costs and effects using a lifetime time horizon.

6.2.1 Evaluations at time of enrolment

For the WCI, trained study staff will administer a brief, validated set of questions to all mothers at the time of enrolment (may be delayed to within 48h of admission). Study staff will also collect socioeconomic data at this time using standardised parent interviews (see Section 5.5.3).

6.2.2 Evaluations during hospitalisation

For household costs, direct and indirect household costs will be collected prospectively using time-use and expenditure surveys and observation of families during their hospital stay. At time of discharge/death, information regarding the time period from admission to discharge will be captured using standardised parent interviews.

6.2.3 Evaluations at follow-up

At the 28-30 day follow-up appointment, trained study staff will readminister the WCI questionnaire to all mothers. In addition, they will ask questions to ensure that costs are captured for the entire neonatal period and to inquire about families' plans going forward.

6.3 Process Evaluation

The process evaluation will be conducted in accordance with the MRC guidance on process evaluation of complex interventions (65) and will integrate both quantitative and qualitative data. In-depth interviews and focus group discussions (FGD) will be undertaken with parents/caregivers, staff, and other key stakeholders as part of the qualitative evaluation to identify experiences of KMC, facilitators and barriers to implementation and complex causal pathways. An iterative approach to qualitative analysis will be used with data collected at several time points and then used to inform later explorations.

6.3.1 Understanding causal pathways for clinical effects

Understanding the causal pathways for clinical effects of the intervention (Objective 2) will be achieved by measurement of the following process outcomes, which are categorised as providing very early (within 24 hours), early (within 72 hours), or late clinical impact:

Very early impact:

- Cardio-respiratory stability within 24 hours post-randomisation
- Prevalence of hypothermia within 24 hours post-randomisation
- Hypothermia density within the first 24 hours post-randomisation
- Prevalence of hypoglycaemia within 24 hours post-randomisation

Early impact:

- Cardio-respiratory stability within 72 hours post-randomisation
- Prevalence of hypothermia within 72 hours post-randomisation
- Hypothermia density within the first 72 hours post-randomisation
- Prevalence of hypoglycaemia within 72 hours post-randomisation
- Presence and severity of IVH within 72 hours post-randomisation

Late impact:

- Presence and severity of IVH at day 7
- Proportion of neonates exclusively breastmilk feeding at discharge
- Presence of late intracerebral sequelae of prematurity (e.g., hydrocephalus, cystic degeneration) at day 28-30

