4.2 Eligibility Criteria for the Trial

Participants must meet the following inclusion criteria and not have any of the exclusion critieria to be able to participate in the trial.

4.2.1 *Inclusion criteria*

- Neonate admitted to JH, MH, EH, IH, or KNRH (inborn or outborn)
- Singleton, twin, or triplet (if triplet pregnancy resulted in demise/stillbirth of one or more fetuses)
- Birthweight $\geq 700\text{g}$ and $\leq 2000\text{g}$
- Chronological age 1-48 hours at time of screening
- Alive at time of recruitment
- Parent/caregiver able and willing to provide KMC
- Parent/caregiver willing to attend follow-up visit
- Indication for KMC “uncertain” according to WHO guideline concerning clinical stability: pragmatically defined as receiving ≥ 1 therapy: oxygen, CPAP, IV fluids, therapeutic antibiotics, phenobarbital

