6.1.2 Evaluations from 24 hours to hospital discharge

All participants will be followed at least daily while admitted to the hospital. Unless otherwise noted, the following data will be collected and recorded in eCRFs daily from 24h through day 7 of life, then weekly on days 14, 21, and 28. If participants are discharged prior to day 7, additional follow-up will be arranged according to study site (see Section 5.8 for additional details).

- a) Participants will receive monitoring of HR, SpO₂, respiratory rate, and axillary temperature every 6h until they meet stability criteria (see Section 3.2.5), after which the frequency of monitoring will transition to daily. Measurements will be recorded in eCRFs. Please refer to Section 8.1 for additional details on clinical monitoring.
- b) Daily review with the following data documented:
 - Date and time of starting to receive breast milk (may be given by nasogastric tube, spoon, syringe, etc)
 - Date and time of starting breastfeeding

- Date that full breast milk feeding is established
- Daily IV fluid volumes and drip rates
- Medications administered each day, including dosage and route of administration
- Therapies administered each day, including flow rate and mode of delivery for neonates receiving oxygen
- Daily measurement of blood glucose (may be discontinued once neonate is tolerating full enteral feeds)
- Compliance with the standardised management protocol and discussion of any deviations with the site paediatrician or medical officer
- Documentation about skin-to-skin contact:
 - Date and time of skin-to-skin contact initiation
 - Duration of skin-to-skin contact/day (hours and minutes) ○ Caregiver providing skin-to-skin contact
 - Whether skin-to-skin contact is temporarily discontinued and date/time of this event
- Documentation of any change in clinical condition warranting temporary cessation of intervention and date/time of temporary cessation
- Identification of any SAE
- Documentation of any reason to suspect mother and/or baby is infected with SARS-CoV-2 (based on signs/symptoms or testing status) for babies recruited after 25 March 2020

c) Weighed on day 5, then daily until discharge (unless deemed too unstable by site study staff); weighing to be in clustered with other activities (e.g., diaper changes)

d) OFC and length will be measured weekly using study-specific equipment

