e) For participants at KNRH and JH, cranial ultrasounds (cUS) will be performed on days 1, 3, and 7 of the hospitalisation, or as an outpatient if discharged before day 7 (see Section 6.1.6 for additional details)

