14.5 Informed Consent

Obtaining informed consent for this RCT may be challenging given the involvement of sick neonates (30); the fact that KMC needs to be started as soon as possible after birth; the fact that some women are not literate; and the fact that some women may be too ill, especially within the first 24 hours, to provide consent or participate. Parental stress is compounded by the fact that complications may be unexpected, especially in low-resource settings, where knowledge of preterm birth is generally low. To help address these issues, this RCT will utilise the continuous consent approach (31), which involves giving parents/caregivers information at multiple time points both before and after recruitment (32). Studies have found that the validity of consent improves when discussion continues after recruitment (31,33). The continuous consent process was utilised in the Total Body Hypothermia (TOBY) trial, which investigated the use of whole-body cooling for neonates with evidence of perinatal asphyxia (92). The continuous consent approach has three main elements (92), all occurring after delivery, which are outlined here in the context of the OMWaNA trial:

1. While a neonate is assessed for eligibility (upon admission to the newborn unit, or the following morning if admission occurs outside normal working hours), parents will be given preliminary information about the trial.
2. If the neonate is eligible, a comprehensive information sheet will be provided and further discussion will take place, including assessment of whether the parents are willing and able to participate. At this point, parents will be asked for their written consent and neonates will be randomised.
3. During the intervention period, the site paediatrician or medical officer will meet with parents to ensure that they understand the trial procedures and wish to continue to participate in the trial. It will be made clear that they may withdraw their baby from the trial at any time.

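### The early IVH outcome is timed from randomisation but the cranial ultrasound scans are timed from admission, so late-randomised babies are observed for only part of the 72-hour window

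*Protocol*

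**What the plan says.** Section 6.3.1 lists, among the early-impact process outcomes, "Presence and severity of IVH within 72 hours post-randomisation". Its clock starts at randomisation.

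Section 6.1.2 says that at KNRH and JH "cranial ultrasounds (cUS) will be performed on days 1, 3, and 7 of the hospitalisation". That clock starts at admission. Section 6.1.6 repeats the days, "cUS will be performed on days 1, 3, 7, and 28-30", without saying what they are counted from. Section 6.1.2 also uses a third count for its routine data, "daily from 24h through day 7 of life, then weekly on days 14, 21, and 28".

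Four other statements bear on the gap between the clocks:
- Section 4.2.1 sets eligibility at "Chronological age 1-48 hours at time of screening" and admits both inborn and outborn babies.
- Section 5.2 asks for eligibility to be assessed promptly on admission.
- Section 14.5 allows assessment on admission, "or the following morning if admission occurs outside normal working hours".
- Section 5.5.1 lists the baseline clinical data without a cranial ultrasound, and Section 5.6 places randomisation after baseline collection.

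The Definitions section notes that most affected infants have no symptoms and that diagnosis rests on screening ultrasound.

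**The concern.** IVH is seen only when a scan is done, so an outcome defined over the first 72 hours after randomisation needs a scan near the end of that period. None is tied to it. Heart rate and oxygen saturation, which feed another early-impact outcome, are by contrast recorded continuously for 72 h from randomisation (Sections 6.1.1 and 8.1).

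Two things follow. First, the stretch of post-randomisation time covered by the day-3 scan differs from baby to baby, so the same outcome label describes different observation periods. Second, the outcome is presence of IVH and no scan has to precede allocation. A bleed that was there before KMC could act is counted as an event. IVH is the only brain marker among the early-impact outcomes, and explaining causal pathways is a stated secondary objective.

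**Working it through.** The plan gives no figure to reproduce on this point. The check is timing arithmetic, followed by a short calculation of dilution.

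**Timing**

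Inputs: scan days 1, 3 and 7 (Section 6.1.2); r = hours from admission to randomisation. The protocol does not state r. I assume 1 to 48 h, bounded by the age limit at screening. Hospital day d is taken as the 24-hour period from 24(d − 1) to 24d hours after admission.

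Formula: scan time after randomisation = scan time after admission − r.

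| Scan | Hours after admission | Earliest (r = 48) | Latest (r = 1) |
|---|---|---|---|
| Day 1 | 0–24 | 0 − 48 = −48 h | 24 − 1 = 23 h |
| Day 3 | 48–72 | 48 − 48 = 0 h | 72 − 1 = 71 h |
| Day 7 | 144–168 | 144 − 48 = 96 h | 168 − 1 = 167 h |

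The day-7 scan always falls outside the 72 h window, so the day-3 scan is the last one that can inform the outcome. Its timing by delay:
- r = 1 to 4 h: 48 − 4 = 44 h to 72 − 1 = 71 h
- r = 16 h (an assumed overnight delay): 32 to 56 h
- r = 24 h: 24 to 48 h
- r = 47 h: 1 to 25 h

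Age at randomisation does not settle the matter. Take two babies both randomised at age 44 h. One admitted at birth (r = 44) has the day-3 scan 4 to 28 h after randomisation. One admitted at age 40 h (r = 4) has it at 44 to 68 h.

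Other day counts do not remove the spread. With calendar days of hospitalisation, day 3 runs from 24 h before to 71 h after randomisation. Counted from birth, with randomisation at age 1 to 48 h, it runs from 0 to 71 h (birth as day 1) or 24 to 95 h (birth as day 0).

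**Bleeds already present at allocation**

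Let the control-arm risk of recorded IVH be a + b, where a is the part present at allocation and b the part arising afterwards. Randomisation makes a equal between arms in expectation. Suppose KMC multiplies b by 0.75. That value is illustrative only: the protocol states no expected effect on IVH. With p = a/(a + b), also not given:

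observed risk ratio = (a + 0.75b)/(a + b) = p + 0.75(1 − p)

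- p = 0.2: 0.2 + 0.60 = 0.80
- p = 0.3: 0.3 + 0.525 = 0.825
- p = 0.5: 0.5 + 0.375 = 0.875

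observed risk difference = (a + b) − (a + 0.75b) = 0.25b, whatever the value of a.

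**The case against.** The strongest reply is that the clocks will usually run close together. Screening is meant to be prompt, and the out-of-hours provision describes an overnight wait, not two days. The 48 h limit is an age limit that also admits outborn babies who arrive late and may be randomised soon after arrival. With prompt randomisation, or a 16 h wait, the day-3 scan is still inside the window and well after allocation. This stands. The protocol gives no frequency of long delays, so the lower end of the 0 to 71 h range shows what the wording permits and not what is typical.

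A reader might infer that the day-1 scan is done before consent in late-randomised babies. The text does not support that: the scans are for participants, and participation requires written consent. In such a baby the hospital day-1 study scan would simply not take place.

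A reader might also infer that counting earlier bleeds biases the comparison, or hides half of the effect. It does neither as a general matter. Those bleeds are balanced in expectation, the risk difference is untouched, and the halving applies only to the ratio at an assumed p of 0.5. Section 10.2.2 fixes effect measures for the primary and secondary outcomes, not for process outcomes.

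Finally, the study schedule figure is not reproduced in the text available, and an analysis plan could define scan windows. The figure may give scan times, but the body text of Sections 6.1.2 and 6.3.1 would still disagree on time zero. An analysis plan can choose among scans already done, but it cannot move them.

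**Conclusion.** The point holds as a minor one. The early IVH outcome and the scans that measure it have different starting points. Followed as written, the day-3 scan may fall anywhere from about 0 to 71 h after randomisation (24-hour hospital days, assumed gap of 1 to 48 h). With a gap of up to 4 h it falls at 44 to 71 h, so the deficiency lies mainly with babies randomised late, whose number is not known from the protocol.

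The absence of a required scan before randomisation means that existing bleeds count as events. This pulls the risk ratio towards 1 by an amount that cannot be sized without p. It does not favour either arm. The outcome is a process measure at the ultrasound sites only. It is in neither the primary nor the secondary list, and the mortality analysis is unaffected.

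**What to change.** Keep the existing scans and change their anchor:

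1. In Sections 6.1.2 and 6.1.6, time the early scans from randomisation. Place the second close to, and not later than, 72 h after randomisation, with a stated window (for illustration, the last 12 hours, 60 to 72 h).
2. Record the date and hour of every scan.
3. Keep presence and severity of IVH as the randomised comparison.
4. Where the first scan was done before or at randomisation, without delaying the start of the intervention, also report new or worsened IVH. Do not treat a scan done after the intervention began as a baseline that removes events, because that would discard early treatment effects.

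The cost is protocol wording and a scan-time field at the ultrasound sites, with no additional scans. The drawbacks are that a scan may move to a different calendar day, and that the new-or-worsened analysis has fewer events and covers only babies with a first scan by randomisation.

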6.3.2 Focus Group Discussions

To examine the barriers and facilitators to initiating KMC before stabilisation to inform uptake and sustainability (Objective 3), we will conduct FGDs with each of the following groups: 1) providers (nurses); 2) parents (intervention and control arms). Each FGD will include 4-8 participants. FGDs conducted will broadly explore barriers and enablers to implementation of KMC before stabilisation and encourage participants to collectively identify potential solutions. Based on findings from the literature (58,59,66) and our feasibility study (56), discussion topics may include perceptions about initiating KMC before stabilisation (e.g., fear of touching small babies or dislodging oxygen masks/IV lines); parent and provider experiences with clinical care and monitoring during KMC and/or incubator care; and implementation experiences in the four hospitals [e.g., staff and peer-counselling (for parents), clinical training and guidelines (for providers), and administrative support].

6.3.3 Interviews

IDIs will be conducted with a random sample of ~24-32 care givers/family members (mother, father, and grandmother) selected from both arms of the trial to explore social and cultural factors (e.g., family/community support, faith, stigma about preterm birth) that may influence maternal coping and compliance with care recommendations. To further inform context specific evidence on the uptake and sustainability of KMC, additional IDIs will be conducted at each site with the following stakeholders: healthcare providers involved in the care of LBW babies (1 paediatrician, 1 medical officer, 2 nurses); hospital leadership (hospital director or administrator). More interviews will be conducted with national leadership (Ministry of Health/Newborn Steering Committee and Uganda Paediatric Association member) and policymakers (WHO, UNICEF and other international bodies that support maternal and child health).

IDIs with a purposive sample of ~16 parents (8 from each arm) whose babies died during the hospital stay will explore parental experiences of trauma and bereavement. The sub-sample from the intervention arm will include parents who experienced a neonatal death while performing KMC. A Ugandan interviewer, who is fluent in Luganda/Lusoga and has experience working in a hospital setting, will receive further training on how to approach sensitive issues prior to conducting any interviews.

[figure not shown]
6.3.4 Additional health systems and clinical data

The following additional health systems and clinical data will be prospectively collected for the process evaluation:

- Admission data for all neonatal unit admissions across the five study sites to observe changes in bed capacity; referral patterns; proportion of preterm/LBW admissions; mortality rates, etc
- Triannual (every 4 months) surveys of staffing, equipment, drug/supply availability, and infrastructure at the 5 study sites
- Biannual (every 6 months) neonatal quality of care survey, including progress monitoring of KMC provision/services (Appendix E) at the five study sites
- Annual documentation of national health delivery, finances and staffing levels, including national survey of neonatal/KMC provision

7. Trial Responsibilities & Management

The OMWaNA trial is a partnership between MRC/UVRI, LSHTM and Makerere, with implementation at four Ugandan hospitals. The host institution is the MRC/UVRI and LSHTM Uganda Research Unit in Entebbe. The trial management structure is outlined in Figure 2.

Figure 2. OMWaNA Trial Management Structure

7.2 Study Team and Infrastructure at Trial Sites

Members of the study team at each site will include 1 study paediatrician/co-investigator (20% effort), 1 study medical officer (full-time), 4 study nurses (full-time), and 1 nurse counsellor (full-time). Study paediatricians will oversee clinical decisions, supervise site staff, and ensure reporting procedures are followed (with support from the trial coordinator). Study medical officers will perform screening, recruitment, and randomisation/allocation procedures. Study nurses will assist with screening and recruitment procedures, collect and record clinical data in eCRFs, and conduct follow-up assessments, including home visits as needed. Nurse counsellors will counsel parents of seriously ill infants. In addition, local newborn unit nurses at each site will receive a stipend to assist with clinical care and data collection/entry.

Substantial expansion of neonatal care capacity and infrastructure has been embedded within the OMWaNA trial. Each hospital has a neonatal unit currently taking referrals from their respective region/district and each led by the paediatrician. The level of equipment in these government facilities differs but all have: warming areas (incubators and/or overhead radiant heaters), oxygen supply (either piped or through concentrators and cylinders), and standard operating procedures for the management of neonates including respiratory distress, apnoea, infection/ sepsis, seizures, hypothermia, and hypoglycaemia (referred to here as 'standard of care'). In addition to the government services available, substantial additional infrastructure will be added to all neonatal units to accommodate the trial. This includes improved facility building infrastructure with all study hospital neonatal care units being restructured to ensure adequate facilities for screening, recruitment and randomisation of infants and facilitation of care of non-trial participants. Site remodelling will include expansion of KMC areas within the neonatal units to ensure that all small and sick newborns, whether in KMC or not, can be cared for

acutely within the neonatal units. Site expansion includes an office for clinical staff and bathrooms and toilets for mothers attending to their babies in the neonatal care unit. All plans include fully functioning sinks in all clinical areas to provide an optimal environment for infection control.

In addition to improved building infrastructure, each unit will be supported with additional staffing and equipment. At each site, a minimum of four additional neonatal research nurses and one Medical Officer will be recruited in partnership with the neonatal Paediatrician and Neonatal Nurse In-Charge at each unit. These will be integrated within the existing staff of the neonatal units and will provide some continuity despite the staff rotations that are common in these government hospitals. Each site will also be supported by the provision of: 6 pulse oximeters (Masimo Rad-8 with neonatal sensors); 1 oxygen concentrator; 2 thermometers; 1 glucose meter and glucose strips; 1 ventilation bag and mask (neonatal size); 1 neonatal weighing scale (Seca 385); 1 neonatal measuring mat (Seca 210); 2-3 paediatric stethoscopes; and a minimum of 4 adjustable KMC beds. In addition, KMC wraps will be provided to support practice in each unit. CPAP will be provided by the duty paediatrician where this is standard of care.

All participating units will receive a comprehensive training programme in neonatal care developed from established UNICEF and WHO protocols including care of the small and sick newborn, feeding and resuscitation. This includes training of neonatal resuscitation (Helping Babies Breathe) and the provision of equipment including neonatal bag and masks and resuscitation mannikins. See sections

5.9.2 “Site staff training on neonatal care and clinical guidelines before start of trial” and 5.9.3 “Refresher trainings throughout trial” for details. Continuous on-the-job support and mentorship will be provided by the resident paediatrician and site co-ordinator, a Ugandan paediatrician with wide experience in newborn care (see below for additional details) specialising in care of the preterm infants.

